## Protocol Summary

This document represents the protocol summary for the study on human subjects. The study will be carried out in accordance with ICH GCP, National Standard of the Russian Federation GOST 52379-2005 "Good Clinical Practice", Helsinki Declaration of World Medical Association, relevant requirements of the regulatory authorities as well as the study procedures.

## Official Title

Comparative Parallel-group Randomized Clinical Trial of Efficacy and Safety of Ergoferon Versus Oseltamivir in the Treatment of Influenza

*Phase:* IV

*Sponsor:* OOO "NPF "Materia Medica Holding", Moscow, Russia

*Protocol No.* MMH-ER-003

## Study purposes

- To assess the efficacy of Ergoferon in the treatment of influenza.
- To compare the efficacy of Ergoferon and Oseltamivir in the treatment of influenza.
- To assess the safety of Ergoferon in the treatment of influenza.

## Outcome Measures

### *Primary Outcome Measure*

1. Proportion of patients with recovery/improvement in health on days 2-7 – according to the patient's diary; on days 3 and 7 – according to objective examination conducted by a physician

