### *Evaluation of sample size*

The sample size was assessed in accordance with the following rules and assumptions:

1. Statistical assumptions:

- 1.1 Lack of clinically relevant superiority of reference product (oseltamivir) over test product (Ergoferon) is assumed, thus statistically meeting Non-Inferiority design:

$$\mathbf{H_0: Ef_{control} - Ef_{test} \geq \delta}$$

$$\mathbf{H_A: Ef_{control} - Ef_{test} < \delta,}$$

where  $\mathbf{Ef_{control}}$  – effect of reference product (oseltamivir),  $\mathbf{Ef_{test}}$  – effect of test product (Ergoferon),  $\delta$  – clinically relevant difference;

- 1.2 Clinically relevant difference value “ $\delta$ ” is considered to be equal to 20% (i.e. Ergoferon effect is supposed to be comparable to the one of oseltamivir if the effect of test product is superior to or inferior to the effect of reference product by no more than 20%);
- 1.3 The power of statistical tests ' $P = (1 - \beta)$ ' is 80% (the probability of correct rejection of the null hypothesis is 0.8);
- 1.4 The probability of type 1 error ' $\alpha$ ' is less than 5% (the probability of false acceptance of the alternative hypothesis is less than 0.05);
- 1.5 Therefore, sample size will be calculated taking into account:
- a. assumption on expected effects declared in the main efficacy criterion of the protocol;
- 1.6 calculation of sample size of groups 1 and 2 for two-sided test for final analysis will be made using the formula:

$$\mathbf{N_1=N_2=(p_a(1 - p_a) + p_b(1 - p_b)) I,}$$

where  $\mathbf{N_1}$  and  $\mathbf{N_2}$  – samples sizes in Ergoferon and Oseltamivir groups

$\mathbf{p_a}$  and  $\mathbf{p_b}$  – expected proportions of the patients with recovery/improvement in these groups

$\mathbf{I}$  – Fisher's information detected using the formula:

$$\mathbf{I=(z_\alpha + z_\beta)^2/(\theta - \delta)^2,}$$

where  $\mathbf{z_\alpha}$  and  $\mathbf{z_\beta}$  – tabular values of z-test for  $\alpha$  and  $\beta$ ,  $\theta$  – difference between proportions ( $\mathbf{p_a - p_b}$ ),  $\delta$  – clinically relevant difference;

- 1.7 final sample size will be determined using the formula:

$$\mathbf{N_F = N / (1 - K_B),}$$

---

 SAS/STAT(R) 9.2 User's Guide, Second Edition.

[http://support.sas.com/documentation/cdl/en/statug/63033/HTML/default/viewer.htm#statug\\_seqdesign sect027.htm](http://support.sas.com/documentation/cdl/en/statug/63033/HTML/default/viewer.htm#statug_seqdesign sect027.htm)

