1.8 where  $N_F$  – final sample size;  $N$  – result of calculation in cl. 1.6, i.e. scheduled number of patients completing the study per protocol;  $C_w$  – withdrawal coefficient.

2. Assumptions on expected clinical study effects:

2.1 The difference between proportions of the patients with recovery/improvement on days 2-7 (according to the patient’s diary) and on days 3 and 7 (according to objective medical examination) in Ergoferon group and Oseltamivir is expected to be  $\geq 0\%$ .

The minimum size of each group will be determined as follows:

Number of patients	Final analysis
Number of patients in both groups	158
including	
- number of patients in Ergoferon groups	79
- number of patients in Oseltamivir group	79

Taking into account that potential withdrawal of 20% patients during the screening and during the study, at least 198 patients (99 in Ergoferon and Oseltamivir group) should sign informed consent.

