**Statistical criteria**

All statistical calculations will be made using two groups of statistical criteria:

- parametric - to evaluate continuous and interval random values;
- non-parametric – to obtain:
  - evaluations on equality/inequality of proportions of the patients upon their comparison for various visits,
  - analysis of frequencies of the features compared,
 and
  - to evaluate continuous and interval random values in case of non-compliance with normal random distribution.

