**Parametric criteria**

Prior to analysis using parametric statistics, data samples under comparison will be tested for normality (the Kolmogorov-Smirnov test).

 **Recovery criteria:** body temperature  $<37.0^{\circ}\text{C}$  + no symptoms.

**Improvement criteria:** body temperature  $\leq 37.2^{\circ}\text{C}$  + total symptom score (except for fever index)  $\leq 2$  scores.

The following parameters and approaches are to be used:

1. To evaluate the differences in continuous variables from two different (independent) groups – Student’s test for independent samples.
2. To evaluate differences in continuous variables in one group at two different visits - Student’s test for paired samples.
3. To evaluate time changes in parameters compared - analysis of variance (ANOVA) or modified repeated measures covariance (ANCOVA).
4. In case of multiple comparisons of the groups various corrections for multiplicity will be used, e.g. Dunnett, Tukey, Scheffe, Holm adapted test, etc.
5. In case of abnormal data distribution generalized linear models and/or mixed linear models will be used.
6. Selection of the type of distribution, specification of factor and covariance structures of the model will be made using fit-statistics such as AIC (Akaike information criterion).

The following SAS software programs are supposed to be applied to the above listed tests and techniques:

- UNIVARIATE: normality verification of the distributions under comparison
- CORR, MEANS - calculation of descriptive statistics
- TTEST – Student’s test with all modifications
- GLM – generalized linear models for analysis of time changes (ANOVA, ANCOVA)
- GENMOD – generalized linear models
- MIXED – mixed linear models.

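### The primary outcome spans eight proportions, but the plan names no deciding readout or success rule; its alpha and 80% power are supported for one comparison only

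*Combined protocol and SAP*

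**What the plan says.** Under Outcome Measures, the single primary outcome is recovery/improvement "on days 2-7 – according to the patient's diary; on days 3 and 7 – according to objective examination conducted by a physician". Under Evaluation of sample size, item 2.1 repeats the same set when it states the expected effect: diary days 2-7, then "and on days 3 and 7 (according to objective medical examination) in Ergoferon group and Oseltamivir is expected to be" at least 0%.

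The rest of that section is written for one comparison. Item 1.1 has one hypothesis pair and item 1.2 one margin of 20%. Item 1.3 sets power ("the probability of correct rejection of the null hypothesis is 0.8") and item 1.4 sets alpha ("the probability of false acceptance of the alternative hypothesis is less than 0.05"). Item 1.6 uses one p_a and one p_b, defined as "expected proportions of the patients with recovery/improvement in these groups", with no value, day or rater attached.

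The direction of the test is not consistent. Item 1.1 is one-sided, item 1.2 describes comparability in both directions, and item 1.6 says "calculation of sample size of groups 1 and 2 for two-sided test for final analysis will be made using the formula".

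Three items come near a rule:
- Parametric criteria, item 4: "In case of multiple comparisons of the groups various corrections for multiplicity will be used, e.g. Dunnett, Tukey, Scheffe, Holm adapted test, etc".
- Non-parametric tests, item 4: the Cochran-Mantel-Haenszel test, described as a chi-square for multiple comparisons on independent strata.
- Non-parametric tests, item 5: survival analysis for repeated presence/absence data, in a list introduced as potential comparisons.

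**The concern.** A non-inferiority claim needs one decision. Eight correlated proportions can give eight different answers, and the plan does not say how they become one. Possible rules include any one passing, all passing, a particular day and rater, or an average over days. These have different error rates and different power, and they can disagree on the same data.

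The trial is open-label and the diary is patient-rated, so a rule left open until analysis could be settled with results in view. The stated alpha and power would then describe one test, and not the primary outcome as written.

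**Working it through.** **Inputs from the documents.** Readouts: 6 diary days + 2 physician visits = 8. Margin δ = 0.20. Expected difference of at least 0, taken as θ = 0. Power 80%, alpha below 5%, 79 completers per arm, 158 in total, 198 consents. **Assumed, because the documents give none:** daily rates and the correlations between readouts.

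**1. The plan's own size.** N per arm = [p_a(1−p_a) + p_b(1−p_b)] × (z_α + z_β)² / (θ−δ)², with z_β = 0.8416. At a 50% rate in both arms:
- one-sided 5%: 0.50 × (1.6449 + 0.8416)² / 0.04 = 77.3, so 78;
- one-sided 2.5%: 0.50 × (1.96 + 0.8416)² / 0.04 = 98.1, so 99.

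At one-sided 2.5%, 79 per arm requires p(1−p) = 79 × 0.04 / (2 × 7.849) = 0.201, a rate of about 28% or 72%. So 79 fits a single test at about 50% with one-sided 5%, or at about 28% or 72% with one-sided 2.5%. The plan does not say which. Withdrawal reproduces: 158 / 0.8 = 197.5, so 198. The formula has no term for several readouts.

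**2. Power of one readout at 79 per arm and a 50% rate.** Φ(0.20/√(2 × 0.25/79) − z_α):
- one-sided 5%: Φ(2.514 − 1.645) = 81%;
- one-sided 2.5%: Φ(2.514 − 1.960) = 71%.

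**3. Eight readouts.** Trials were simulated with 79 per arm and an unpooled Wald test of each readout against 0.20. Physician rates were set equal to same-day diary rates. Two patterns were run:
- status may change from day to day: latent day-to-day correlation 0.5 to 0.85, physician-diary correlation 0.8;
- recovery is lasting: once recovered, a patient stays so in the diary; physician-diary correlation 0.8 to 0.95.

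Rates on days 2-7 were 12/30/50/65/80/90% (gradual), 3/8/15/25/80/92% (steep) and 50% throughout (flat). Ranges cover both patterns.

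| Quantity | One-sided 5% | One-sided 2.5% |
|---|---|---|
| Equal arms, some but not all pass: gradual and steep curves | 17-46% | 27-63% |
| Same, flat 50% (low end: lasting recovery) | 22-71% | 28-85% |
| Power if all eight must pass: gradual | 54-67% | 37-52% |
| Same, flat 50% | 29-70% | 15-57% |
| Same, steep | 81-83% | 70-73% |
| False success if any one suffices, uncorrected, true deficit 20 points on every readout | 9-31% | 5-18% |

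The last row needs curves on which a 20-point deficit is possible, which excludes days with rates of 3-15%. It uses oseltamivir rates of 25/35/50/65/80/90%, 50% throughout and 60% throughout. The low ends come from lasting recovery at flat rates, where the diary days carry the same information.

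**4. A larger analysis set.** If all 198 consented patients entered the Full Analysis Set, there would be 198 / 2 = 99 per arm. All-eight power on the gradual curve with day-to-day changes would then be about 70-75% / 56-62%.

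**The case against.** The strongest reply is that the plan intends one comparison. Item 2.1 speaks of the difference in the singular, and the formula has one pair of proportions. That may be so, but then the plan does not say which comparison it is, and the gap remains.

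A second reply is that multiplicity is covered. The three items quoted or described above do mention corrections or repeated measures, so it would be wrong to say the plan is silent. None supplies the rule. The list of corrections selects no method and sits under parametric criteria, while proportions are assigned to the non-parametric group. The Cochran-Mantel-Haenszel item is for independent strata, and repeated days on the same patients are not independent. Survival analysis is only a potential method, and no margin is given on its scale.

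Three stronger readings are tempting and are not supported:
- *The plan foresees several primary tests*, because Statistical criteria mentions "evaluations on equality/inequality of proportions of the patients upon their comparison for various visits". That is generic wording. It fits the secondary proportions equally well and may mean comparison between visits.
- *All eight must pass*, because item 2.1 joins them with a conjunction. That sentence states an expected effect and is not a decision rule.
- *Type I error is inflated as the plan stands.* Inflation follows only under an uncorrected any-of-eight rule, which the plan does not adopt. An all-eight rule would keep alpha and cost power instead.

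It is also fair to say that the sizes depend on the model. A flat 50% with daily switching is an unlikely recovery pattern and gives the widest figures. Lasting recovery narrows them considerably, and at 2.5% per test any-of-eight false success can be as low as about 5%. Finally, the document calls itself a protocol summary, so a fuller document might hold the rule. The finding is that the public text does not state it.

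**Conclusion.** The concern holds and should be resolved before analysis. That the rule is absent from the public text needs no modelling assumption. The plan's alpha and 80% power are supported for one comparison, whose day, rater and rate are not given.

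The size of the consequence does rest on assumed rates and correlations, so the simulated ranges are illustrations and not bounds. They show that partial passing is common enough for the choice of rule to decide many trials, even with truly equal arms. They also show that an all-eight rule would usually miss 80% power at 79 per arm, with the steep curve at one-sided 5% as the exception. The point does not show that 79 per arm is wrong for a single readout.

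**What to change.** Name one primary readout for the non-inferiority test and make the others secondary. There are two workable forms:
- **One prespecified day and rater, with a reason.** State the assumed rate and restate the power at 79 per arm. At a 50% rate this is about 81% at one-sided 5% and about 71% at one-sided 2.5%, so the stated power or the size may have to change.
- **One risk difference averaged over diary days 2-7.** The margin must be justified on that scale: 0.20 × 6 = 1.2 fewer recovered/improved days per patient. At 79 per arm, power was 95-100% / 90-100% on the three curves when status could change daily. If each patient had the same status on all six days, it would fall to the single-day figure. Averaging also hides early-versus-late differences.

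If all eight stay primary, prespecify the rule (all-eight, Holm or a fixed order) and restate the power for it. With day-to-day changes in status, 80% power for all-eight needs about 110-120 / 130-140 per arm on the gradual curve and 140-160 / 170-180 at a flat 50%. On the steep curve, 79 is enough at one-sided 5% and 99 at 2.5%.

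As a linked correction, reconcile items 1.1, 1.2 and 1.6 on the direction of the test and state the one-sided alpha used.

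No new data are needed to name one readout. The costs are a reasoned choice and, possibly, a lower stated power.

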### *Secondary Outcome Measures*

2. Fever changes over time (body temperature change on days 2-7 compared to baseline).
3. Average duration of fever.
4. Proportion of subjects with normal body temperature (below 37,0^0C) on days 2-7.
5. Severity of clinical manifestations of influenza (fever, general symptoms and nasal/throat/chest symptoms) in scores on day 1-7 – according to the patient's diary; on days 1, 3 and 7 – according to objective examination by the investigator.

---

 **Recovery criteria:** body temperature <37.0^0C + no symptoms.

**Improvement criteria:** body temperature ≤37.2C + total symptom score (except for fever index) ≤2 scores.

 Criteria of no fever - body temperature lower than 37.0° C for 24 hours.

6. Duration of the major clinical symptoms of influenza (fever, general symptoms and (nasal/throat/chest symptoms) in days (according to the patient diary).
7. Severity of influenza course (based on area under curve for total influenza severity score on days 1-7 – according to the patient diary; on days 1, 3 and 7 – according to objective examination by the physician).
8. Proportion of patients, who used antipyretics on days 1, 2, 3, 4 and 5 of the treatment.
9. Proportion of patients with complications requiring antibiotics, aggravation of the disease (severe influenza).
10. Proportion of patients with negative results of virology assay on days 3, 5 and 7 (based on PCR of nasopharyngeal swabs).
11. Dynamics of Parameters of Immune Status (T-cell and B-cell Immune Response) on days 1, 3 and 7 of the observation:
  - Concentration of regulators of the T-cell immune response (IL2, IFN  $\gamma$ , IL-18), and regulators of B-cell immune response (IL-4, IL-16).
12. Dynamics of Parameters of Immune Status ( IFN- $\alpha$  and IFN- $\gamma$  Production) on days 1, 3 and 7 of the observation:
  - Level of spontaneous and induced production of IFN- $\alpha$  and IFN- $\gamma$  by leukocytes (in vitro).
13. Dynamics of Parameters of Immune Status (Absolute Number of Each Type of White Blood Cells and Different Lymphocyte Phenotypes) on days 1, 3 and 7 of the observation:
  - The absolute number of each type of white blood cells (WBC): Absolut Count (AC) of leukocytes, neutrophils, lymphocytes, monocytes, eosinophils, basophils, and CD3, CD4, CD8, CD4/CD8, CD16, CD119 leukocytes.
14. Dynamics of Parameters of Immune Status (relative percentage of each type of white blood cells and different lymphocyte phenotypes) on days 1, 3 and 7 of the observation:
  - The relative percentage of each type of white blood cells (WBC): Relative Count (AC) of leukocytes, neutrophils, lymphocytes, monocytes, eosinophils, basophils, and CD3, CD4, CD8, CD4/CD8, CD16, CD119 leukocytes.

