## **Study design**

Study design: an open-label, comparative, randomized, parallel group clinical study to evaluate efficacy of the study treatment.

The study will enroll outpatient subjects of either gender aged 18-70 years old inclusively with clinical manifestations of influenza during seasonal morbidity seeking medical advice within the first two days of the disease.

After signing informed consent to participate in the clinical study baseline examination will be initiated including nasal swab for rapid diagnosis and verification of influenza as the cause of the disease. In case of positive result of immunochromatographic test the patient will be enrolled. In case of negative result of rapid test the patient will be enrolled provided that (1) he/she has clinical manifestations of typical influenza; (2) the history evidences contact with a patient with influenza; (3) the region has influenza epidemics. Additionally, at the screening (Day 1) all patients regardless of the results of rapid test will provide nasopharyngeal swabs for further PCR diagnosis and identification of RNA of influenza A and B virus, thermometry, history collection, evaluation of vital signs, physical examination will be performed and concomitant therapy will be recorded. Females of childbearing potential will undergo pregnancy test. If inclusion criteria are met and non-inclusion criteria are absent (Day 1) the patient will be enrolled in the trial and randomized into one of the two groups: group 1 will receive Ergoferon as per the selected dosing regimen for 5 days; group 2 will be treated with Oseltamivir at 75 mg twice a day for 5 days.

At Day 1 visit the patient will receive the study product and an antipyretic product approved by the study protocol.

The patient will receive the diary in which he/she will have to record axillary body temperature (measured by non-mercuric Geratherm Classic thermometer ) in the morning and evening as well as intensity of the disease symptoms and number of doses of the antipyretic product. The investigator will train the patient concerning the diary filling.

In total 3 visits (Days 1, 3 and 7) will be made by the patient/investigator during the treatment and follow-up period, on day 5 an additional visit will be made for nasopharyngeal swabs.

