## **Inclusion and exclusion criteria**

### ***Inclusion criteria***

1. Patients aged from 18 to 70 years.
2. Patients who were admitted to hospital within 48 hours from the onset of influenza signs.
3. Patients with body temperature  $\geq 37.8^{\circ}\text{C}$  when visiting a doctor + severity of influenza symptoms  $\geq 4$  scores (presence of at least one general symptom  $\geq 2$  scores and 1 nasal/throat/chest symptom  $\geq 2$  scores or greater number of symptoms with the severity  $\geq 1$  point).
4. Diagnosed influenza confirmed by rapid diagnostic test (OSOM Influenza A&B Test).
5. The possibility to start therapy after the onset of the first symptoms of influenza.
6. Usage of contraceptive methods by both gender patients of reproductive age during the trial and within 30 days after ending the participation in the trial.
7. Availability of signed patient information sheet (Informed Consent form) for participation in the clinical trial.

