### Study design scheme

### Schedule of study procedures

Procedure/visit	Day 1	Day 3	Day 5	Day 7
Obtaining informed consent (signing informed consent by the patient)	+			
Collection of complaints	+	+		+
Collection of medical history data	+			
Objective examination	+	+		+
Recording influenza symptoms in scores	+	+		+
Collection of nasal swabs and isolation of influenza agent antigens	+			
Collection of nasopharyngeal swab for PCR diagnosis	+	+	+	+
Pregnancy test	+			
Information on concomitant medicines	+	+		+

Inclusion/exclusion criteria	+			
Randomization and prescription of study therapy	+			
Antipyretic drug dispensing	+			
Blood sampling for immunological tests	+	+		+
Dispensing of the study drug	+			
Drug accountability and return, assessment of compliance				+
Distribution of diaries	+			
Evaluation of correct diary filling		+		+
Diary return				+
Evaluation of therapeutic safety		+		+

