## Statistical Analyses

### *Samples*

Total set comprised all enrolled patients whose parents/adopters had signed the informed consent form for participation of a patient in the trial. This sample will consider all adverse events throughout the study, including those occurred prior to the study therapy. Any medically unfavourable events (conditions) recorded in patients from Total set after signing informed consent but before administration of the study product will be considered as concomitant conditions.

Sample of the patients receiving at least one dose of the study product will be used for the study drug safety assessment (Safety population), as any adverse events emerging after administration of the product will be recorded.

Full Analysis Set This sample will consist of all enrolled patients, except for those who met at least one of the following criteria:

- 1) failure to meet inclusion/non-inclusion criteria;
- 2) patient failing to take any dose of the study drug;
- 3) absence of any data on the patient after randomization.

This was the best set for the Intention-to-treat method, so it will be used in the Intention-to-treat efficacy analysis of the test therapy.

Unavailable/missing data (parameters/variants) will be completed by the Last Observation Carried Forward method (LOCF).

Per Protocol set. This sample includes all patients who completed the therapy as per the study protocol, without any missing visits or major protocol deviations. This set will be used in the Per Protocol efficacy analysis of the test therapy.

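### Outcome 10 counts patients already PCR-negative on Day 1, so it measures PCR negativity, not conversion from positive to negative, and dilutes any difference between the arms

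*Combined protocol and SAP*

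**What the plan says.** Outcome 10, under Secondary Outcome Measures, is "Proportion of patients with negative results of virology assay on days 3, 5 and 7 (based on PCR of nasopharyngeal swabs". It names no baseline condition and no denominator.

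Entry is described in two ways. Inclusion criterion 4 requires "Diagnosed influenza confirmed by rapid diagnostic test (OSOM Influenza A&B Test". The Study design section is wider: "In case of negative result of rapid test the patient will be enrolled provided that" the clinical picture is typical, there was contact with a case, and the region has an epidemic. The same section states that "all patients regardless of the results of rapid test will provide nasopharyngeal swabs for further PCR diagnosis". It does not make a positive PCR a condition of enrolment or randomisation, both of which take place on Day 1.

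The schedule lists "Collection of nasopharyngeal swab for PCR diagnosis" on Days 1, 3, 5 and 7, so a baseline PCR status is planned for every patient.

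Under Samples, the Full Analysis Set (FAS) is described thus: "This sample will consist of all enrolled patients, except for those who met at least one of the following criteria". The three criteria are "failure to meet inclusion/non-inclusion criteria", no dose taken, and no data after randomisation. For the Per Protocol set, "This sample includes all patients who completed the therapy as per the study protocol", with no missed visit or major deviation. Neither set refers to PCR, and no PCR-confirmed set is defined. Missing data in the FAS are filled by LOCF.

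**The concern.** A patient with no detectable virus on Day 1 has nothing to convert. If that patient stays negative, outcome 10 records a negative result on Days 3, 5 and 7 whatever the treatment did. Such patients raise the proportion negative in both arms and pull the two proportions together.

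Outcome 10 is the only virological efficacy outcome in a trial that compares the test product with oseltamivir and is planned as non-inferiority. Dilution moves the result toward similarity, so two close proportions would be hard to interpret: they could reflect similar viral clearance, or partly the presence of patients without detectable virus at entry.

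**Working it through.** **Can Day 1 PCR-negative patients reach the analysis?**

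- If the Study design wording governs, rapid-test-negative patients can be enrolled, and some may be PCR-negative.
- If inclusion criterion 4 governs, the first FAS exclusion removes rapid-test-negative patients. Patients who are rapid-positive but PCR-negative remain.
- Under both rules, nothing in the FAS or Per Protocol definition removes a patient because of a negative Day 1 PCR.

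The contradiction therefore affects how many such patients there are, not whether the definition admits them.

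**Inputs.** The plan gives no rate, power or margin for outcome 10, so there is no figure to reproduce. The 79 per arm is the planned number of completers for the primary outcome, borrowed here. Assumed, because the documents are silent: q, the Day 1 PCR-negative share, from 10% to 40%; and Day 3 negativity among Day 1 positives of 30% with Ergoferon and 50% with oseltamivir.

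**Dilution.** Let p be the proportion negative among Day 1 positives and s the proportion negative at the later visit among Day 1 negatives. The reported proportion is P = q·s + (1 − q)·p. If q and s are the same in both arms, the difference is (1 − q)(p_control − p_test). Taking s = 1:

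| q | Ergoferon | Oseltamivir | Reported difference | True difference |
|---|---|---|---|---|
| 10% | 0.10 + 0.90 × 0.30 = 37% | 0.10 + 0.90 × 0.50 = 55% | 18 | 20 |
| 20% | 44% | 60% | 16 | 20 |
| 30% | 51% | 65% | 14 | 20 |
| 40% | 58% | 70% | 12 | 20 |

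The shrinkage depends only on q. An assumed 50% v 70% gives the same four differences.

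**Imbalance in q** (same assumed 30% v 50%, average q of 20%):

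- Ergoferon 25%, oseltamivir 15%: 0.25 + 0.75 × 0.30 = 47.5%; 0.15 + 0.85 × 0.50 = 57.5%; gap 10 points.
- Balanced at 20%: gap 16 points.
- Ergoferon 15%, oseltamivir 25%: 0.15 + 0.85 × 0.30 = 40.5%; 0.25 + 0.75 × 0.50 = 62.5%; gap 22 points.

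This imbalance moves the gap 6 points either way from the diluted value. With 79 per arm and q = 20%, the standard error of the difference in q is √(2 × 0.20 × 0.80 / 79) = 6.4 points. A 10-point imbalance in one given direction is thus 10/6.4 ≈ 1.57 standard errors, roughly a 6% chance.

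**Effect of restricting to Day 1 positives.** Two-sided 5% test, normal approximation: power = Φ[(d − 1.96·SE₀)/SE₁], where d is the difference, SE₀ uses the pooled proportion and SE₁ the separate ones. At q = 20% as written (44% v 60%, n = 79): SE₀ = 0.0795, SE₁ = 0.0785, (0.16 − 0.1558)/0.0785 = 0.05, power 52%. Restricted (30% v 50%, n = 0.80 × 79 ≈ 63): SE₀ = 0.0873, SE₁ = 0.0854, (0.20 − 0.1711)/0.0854 = 0.34, power 63%.

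| q | n per arm, restricted | Power as written (n = 79) | Power restricted |
|---|---|---|---|
| 10% | 71 | 62% | 68% |
| 20% | 63 | 52% | 63% |
| 30% | 55 | 43% | 57% |
| 40% | 47 | 35% | 51% |

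The direction is the same for the other assumed pairs tried. At q = 20%, 50% v 70% gives 58% as written and 63% restricted; 70% v 90% gives 79% and 81%.

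**LOCF.** For a missed Day 3 swab the only earlier PCR result is Day 1. If that value may be carried forward, a baseline negative becomes a Day 3 negative without a swab.

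**The case against.** The strongest objection is that the size of the effect is unknown and may be small. Inclusion criterion 4, if it governs, leaves only rapid-positive/PCR-negative patients, and exclusion criterion 3 screens out suspected illnesses that resemble influenza. Neither q nor the negativity rates are in the documents, and at q = 10% a 20-point gap still shows as 18. This stands as a limit on size. It does not close the gap in the definition, because neither criterion refers to PCR.

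A false-negative first swab could also turn positive later. That changes the reported levels, but the difference is still multiplied by (1 − q) as long as Day 1 negatives behave alike in both arms.

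The LOCF point is conditional. The plan does not say whether a Day 1 value may be carried into a post-baseline outcome, and the Per Protocol set has no missed visits.

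A reader might infer more than the documents support:

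- That the outcome hides a difference. It dilutes one, by a factor that may be close to 1.
- That every negative swab is counted. The outcome counts patients at each day.
- That a 25% v 15% imbalance alone halves the gap. Of the 10 points lost, 4 are dilution and 6 imbalance, and the reverse imbalance widens the gap to 22.
- That the trial's non-inferiority conclusion is compromised. The 20% margin and the sample size belong to recovery/improvement. Outcome 10 is one of 13 secondary outcomes, with no margin and no equivalence claim, and the plan does not call it clearance.

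**Conclusion.** The point holds as a defect of definition. Followed as written, outcome 10 is the share of patients who are PCR-negative on a given day, and it includes any who were negative before treatment. It cannot be read as conversion from positive to negative.

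For equal q, dilution by (1 − q) is exact provided Day 1 negatives behave alike in both arms. Its size cannot be fixed from the documents: the range of 18 down to 12 points rests on assumed q of 10% to 40%. The imbalance figures also rest on the assumed 30% v 50% and on Day 1 negatives staying negative. Imbalance is random error, not a systematic push toward similarity. Since the outcome is secondary, this is worth correcting but does not threaten the primary analysis.

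**What to change.** Define outcome 10 as the proportion PCR-negative on Days 3, 5 and 7 among patients whose Day 1 PCR was positive for influenza A or B. Report Day 1 PCR status by arm, and keep the all-patient proportion as supportive. State whether a Day 1 result may be carried into Day 3. Reconcile the Study design section with inclusion criterion 4, so that the population entering this outcome is clear.

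The change takes a few lines and no new sampling, because the Day 1 swab is already planned for all patients. It is taken at screening, before treatment, so restricting on it keeps the randomised comparison valid.

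The cost is a smaller denominator, (1 − q) of each arm: about 63 of 79 at q = 20% and 47 of 79 at q = 40%. That is not a slight loss if q is large, but in the scenarios above the undiluted difference more than made up for it in power.
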